If the patient's decisional capacity is impaired, but the treating Stroke Neurologist deems the patient capable of assenting to study participation, then the patient and their LAR will be included in the informed consent process. In this case, enrollment will proceed only if the patient assents and the LAR gives consent to study enrollment. In the event that the participant is decisionally impaired to the point where both consent and assent cannot be obtained for the study, consent will be obtained from the LAR. In any other situation where the patient is deemed not to have the capacity to consent, the decision will be made not to enroll the patient in the study. All clarifications will be handled directly by the principal investigator.

The use of an LAR will be documented on the data collection form. Enrollment into the study after the informed consent process is completed will be documented in the medical record. In the event that an LAR consents on behalf of a patient lacking capacity, continuing informed consent will be obtained if the treating physician or study physician determines that the patient regains the capacity to consent during the course of the protocol. Assessment for regaining capacity to participate in the informed consent process will be performed at each study visit.

STATISTICAL ANALYSIS

Descriptive statistics (mean \pm standard deviation and median for continuous data such as age; frequencies and percentages for categorical data such as gender, medical history, etc) will be calculated for baseline patient characteristics.

The incidence of AF will be calculated as the total number of patients with AF in 12 months divided by the total number of patients studied, along with the corresponding 95% confidence interval.

The analysis of “time-to-first-documented-AF” will be accomplished by applying standard methods of survival analysis, i.e., computing the Kaplan-Meier¹ product limit curves. In cases where the endpoint event, “AF”, had not yet occurred, 12 months will be used and considered ‘censored’. The median rate will be obtained from the Kaplan-Meier/Product-Limit Estimates and its corresponding 95% confidence interval will be computed, using Greenwood’s formula² to calculate the standard error.

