Univariate analyses will be performed to screen for potential predictors of AF. The chi-square test or Fisher’s exact test, as deemed appropriate, will be used to compare AF patients with non-AF patients for categorical variables and the two-sample t-test or Mann-Whitney test for continuous data.

As a possible secondary analysis, those factors that appear to be associated with AF in the univariate analysis ($p < 0.25$) will be included in a logistic regression model. Backwards selection will be used to remove variables that do not significantly contribute information to the model, given other factors included in the model. A receiver operating characteristic (ROC) curve will be constructed to look at the final model’s ability to predict AF. A numerical measure of the accuracy of the model will be obtained from the area under the curve (AUC), where an area of 1.0 signifies near perfect accuracy, while an area of less than 0.5 indicates that the model is worse than just flipping a coin. The following will be used as a guide for AUC:

0.9-1.0	Excellent
0.8-0.9	Very good
0.7-0.8	Good
0.6-0.7	Average
0.5-0.6	Poor

The Hosmer and Lemeshow Goodness-of-Fit test will also be used to test how well the model fits the data.

Unless otherwise specified, a result will be considered statistically significant at the $p < 0.05$ level of significance. All analyses will be performed using SAS (SAS Institute, Cary, NC).

DISCOMFORTS AND RISKS

The risks to the subjects are low in relation to the anticipated benefits of detecting paroxysmal AF, which will change the strategy of secondary stroke prevention from antiplatelet to anticoagulation

¹ Lee, E. T. (1992), *Statistical Methods for Survival Data Analysis*, Second Edition, New York: John Wiley & Sons.

² Greenwood M. (1926), *The Errors of Sampling of the Survivorship Table*, Vol. 33 of Reports on Public Health and Medical Subjects. London: Her Majesty’s Stationery Office

therapy and reduce the annual risk of recurrent stroke by allowing earlier treatment once AF is detected. The procedural risks have been reviewed under the section (“Design: Reveal LINQ Insertable Cardiac Monitor)

Potential risks and discomforts associated with receiving a Reveal LINQ ICM device include:

- Local site bleeding
- Temporary discomfort at the implant site.
- Rejection of the device by the body, which may have symptoms such as swelling, redness, or other irritation at or near the implant site

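### The default p<0.05 rule covers every AF-predictor comparison and the backward-selected model, with no candidate list, no multiplicity adjustment and no exploratory label

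*Combined protocol and SAP*

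**What the plan says.** All the relevant text is in the Statistical Analysis section of the combined protocol and SAP.

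- Purpose of the comparisons: "Univariate analyses will be performed to screen for potential predictors of AF".
- Tests for categorical variables: "The chi-square test or Fisher’s exact test, as deemed appropriate, will be used to compare AF patients with non-AF patients". Continuous variables get a t-test or Mann-Whitney test.
- Model entry: "those factors that appear to be associated with AF in the univariate analysis ($p < 0.25$) will be included in a logistic regression model". This step is optional; the sentence opens with the words "As a possible secondary analysis".
- Model reduction: "Backwards selection will be used to remove variables that do not significantly contribute information to the model, given other factors included in the model". No numeric level for staying in the model is given.
- Significance: "Unless otherwise specified, a result will be considered statistically significant at the $p < 0.05$ level of significance".

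The candidate predictors are not listed. The nearest text describes baseline summaries, with age as the continuous example and, for the rest, "frequencies and percentages for categorical data such as gender, medical history, etc". The section has no multiplicity adjustment, no ordering of the comparisons and no statement that they are exploratory.

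**The concern.** The primary analysis is a proportion with a 95% confidence interval, and time to first AF is a Kaplan-Meier estimate. Neither is a hypothesis test. The 0.05 sentence therefore acts almost entirely on the predictor work; the only other test named is the Hosmer-Lemeshow goodness-of-fit test. Each univariate comparison carries its own 5% chance of a false positive, and the number of comparisons is left open. The terms left after backward selection are then judged on the same data that selected them, so their p-values no longer carry their nominal meaning.

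At stake is how a reported predictor is read. With 75 patients and an open list, some variable may well cross 0.05 by chance, and the plan's own rule would call it significant. The section also grades the final model's AUC on a scale whose top band is excellent, which invites readers to take the result as evidence of prediction.

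**Working it through.** **No plan figure to reproduce.** The documents state no number of predictors, no expected AF rate in this population, no predictor prevalences and no family-wise error rate.

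**Inputs from the documents.** Sample size 75 (Follow Up). Significance level 0.05; sidedness is not stated, so two-sided is assumed. Entry level 0.25. Eight co-morbidities in the eligibility criteria: sleep apnea, coronary artery disease, COPD, hyperthyroidism, BMI above 30, prior MI, prolonged PR interval and renal impairment. These are eligibility items, not named predictors, but they are plausible candidates.

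**Assumed inputs.** AF rate of 10%, 20% or 30%, that is 75 × 0.10 = 7.5, 75 × 0.20 = 15 or 75 × 0.30 = 22.5 cases on average. Candidate count of 8 (the co-morbidities alone) or 15 (adding virtual CHADS2, its likely components, age, sex and etiology). Prevalences of 5-80% and a common correlation of 0 to 0.5 for the 15-candidate table below.

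**Step 1: idealised independent tests.** The chance of at least one p<0.05 among k null tests is 1 − 0.95^k.

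- k = 6: 1 − 0.735 = 26.5%
- k = 8: 1 − 0.663 = 33.7%
- k = 12: 1 − 0.540 = 46.0%
- k = 15: 1 − 0.463 = 53.7%

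Correlation lowers this. For two-sided z tests at correlation 0.5 it is 25.2% for k = 8 and 36.2% for k = 15. Fisher's exact test, which is conservative in small cells, lowers it further, so the planned tests were simulated.

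**Step 2: simulation with 15 candidates** (13 binary, 2 continuous; n = 75; AF independent of all candidates; Fisher's test when any expected count is below 5, otherwise chi-square; t-test for continuous; p<0.25 entry, then backward elimination at 0.05; up to 1,500 trials per cell). Each cell gives the percentage at correlation 0 / 0.2 / 0.5.

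| AF rate | Any univariate p<0.05 | Final model keeps a noise term |
|---|---|---|
| 10% | 35.7 / 32.0 / 26.9 | 35.2 / 32.0 / 27.6 |
| 20% | 40.9 / 39.2 / 31.2 | 41.1 / 37.8 / 35.5 |
| 30% | 45.9 / 45.1 / 39.1 | 43.0 / 42.8 / 42.8 |

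Repeating the univariate stage with other assumed prevalences gave 33 / 28% at a 10% AF rate, 41 / 34% at 20% and 47 / 38% at 30% (correlation 0 / 0.5). A further run gave 28-48%. Taken together, the range is about 27-48%.

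**Step 3: eight binary candidates only.** With Fisher's test where cells are small, separate runs gave 16-24%, 16-25% and 16-27%. With uncorrected chi-square throughout, the figure is 27-34%. The plan leaves the choice between the two tests open.

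**Step 4: final model with fewer candidates** (AF rate 10-28%, 600 trials per setting, Monte Carlo error about 2 points). At least one false term was kept in about 19-23% of trials with 8 candidates, 25-30% with 10 and 27-39% with 12. Model-stage figures are approximate: some sparse-data fits did not converge, and those in the table rest on the 94-98% of trials whose fits completed.

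**Relative to one test at 5%:** 16/5 = 3.2 and 48/5 = 9.6, so roughly three to ten times.

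**The case against.** The strongest reply is that nothing confirmatory is at risk. The Objectives section lists one primary and four secondary objectives, and none concerns predictors of AF. The plan says it is screening for potential predictors and calls the model a possible secondary analysis. Family-wise control is not the obvious standard for a screen in a 75-patient single-center cohort. This stands, and it limits the point to interpretation and reporting. It does not remove it, because those words describe purpose and do not restrict the significance sentence.

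A second reply is that the univariate stage does specify another criterion, 0.25, and that the 0.05 level for staying in the model is only inferred. Both observations are fair. But 0.25 is stated for entry to the model, and 0.05 is the plan's only definition of significant, which is the term its removal rule relies on ("Backwards selection will be used to remove variables that do not significantly contribute information to the model"). Even if the univariate stage were exempt, the model terms would still fall under the 0.05 rule.

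A third reply is that the count of 15 is constructed: it includes a score together with its likely components, which the documents do not list, and coronary artery disease overlaps with prior MI. This also stands, and it is why the result is given as a range across counts.

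**Conclusion.** The point holds as a limited one. The plan applies an unadjusted 0.05 rule to an open list of predictor comparisons and, by default, to terms selected on the same data, without saying that these are exploratory. Under the stated assumptions, the chance of at least one false significant univariate predictor is about 16-27% with the eight co-morbidities and about 27-48% with 15 candidates.

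A reader might go further in three ways that the documents do not support.

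- That a particular false-positive rate is a property of the plan. It is not: candidate count, AF rate, prevalences and correlation are all assumed, and other choices move the figure in both directions.
- That the main result is compromised. The AF proportion and its confidence interval do not depend on these tests.
- That a chance predictor would decide who receives an implanted monitor. The Introduction ties a change in practice to the incidence found, not to predictors.

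**What to change.** In the Statistical Analysis section:

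1. Amend the 0.05 sentence so that it does not apply to the univariate predictor comparisons or the backward-selected model.
2. State that these analyses are exploratory and that no predictor will be declared statistically significant from them, including from p-values in the selected model.
3. List the candidate predictors before the data are analyzed.
4. Report every candidate tested, whether or not it enters the model, with its effect estimate and 95% CI.

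Because the removal rule takes its level only from the 0.05 sentence, the amended text should also give a numeric stay level, described as a model-building rule and not as a test of significance. A formal multiplicity correction is not needed for a screening analysis presented this way.

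The cost is a few sentences, with no new patients or data. The downside is that no predictor can be called significant from this study; any association would need confirmation elsewhere.

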Anticoagulation is the treatment of choice for AF and paroxysmal AF.¹³ Anticoagulation in patients with paroxysmal or chronic AF reduces the risk of stroke by 64% and death by 25%.⁵ The identification of paroxysmal AF in EMBRACE (30 day) and SURPRISE (mean 133 days) led to a change in management to full anticoagulation in 13% and 18% of patients, respectively. In the Crystal AF study, 97% of patients who were diagnosed with AF were changed to oral anticoagulants.⁸ It is postulated that in the era of the novel oral anticoagulants, the detection of AF and the appropriate initiation of anticoagulation as secondary stroke prevention will reduce the risk of recurrent ischemic stroke without increasing the rates of symptomatic intracerebral hemorrhage or systemic hemorrhage. For patients with a presumed stroke mechanism other than AF who are found to have silent PAF, a change in management to full anticoagulation could have similar effects.

OBJECTIVE(S)/SPECIFIC AIMS AND HYPOTHESES

Primary Objective:

To determine the incidence of paroxysmal atrial fibrillation (AF) in ischemic stroke patients who have a presumed known stroke etiology other than atrial fibrillation.

Secondary Objectives:

- 1. Percentage of patients who are diagnosed with AF who are changed to anticoagulant therapy.**
- 2. Duration and frequency of AF episodes.**
- 3. Percentage of asymptomatic AF episodes.**
- 4. Incidence of recurrent ischemic stroke.**

SUBJECT SELECTION – ELIGIBILITY CRITERIA

The subject population will include patients with a diagnosis of Ischemic stroke. A total of 75 patients will be enrolled over a **2-year period**.

Inclusion Criteria:

Patients with a recent ischemic stroke or TIA with brain infarction on brain imaging.

1. No history of atrial fibrillation or finding of atrial fibrillation on standard inpatient monitoring (ECG, telemetry, 24-hour Holter monitor)
2. Have a presumed stroke etiology: Lacunar or small vessel thrombosis, extra-cranial or intracranial atherosclerotic stenosis or dissection, arteriopathy or vasculitis, hypercoagulable state, aortic arch plaque with or without mobile elements, or evidence of a low-risk cardiac source (e.g., PFO with or without atrial septal aneurysm and with or without evidence of venous thromboembolic source).

The following diagnostic tests are minimally required to determine the stroke etiology:

- Brain MRI
- 12-lead ECG for AF detection

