Device recording of an AF episode of at least 2 minute duration will be required to diagnose a patient with AF. A partial device transmission (summary of potential AF episodes) will be automatically downloaded daily via the Medtronic MyCareLink patient monitor and the study cardiologist will receive an alert within 24-48 hours if the computer monitoring system confirms an episode to be probable AF. Participants may also use the Reveal Patient Assistant to activate recording of cardiac information in the Reveal LINQ ICM while experiencing or immediately after a symptomatic event. Participants will be required to perform a manual device interrogation on a monthly basis. All downloaded rhythms will be manually reviewed every month for each enrolled patient by the study cardiologist. Each AF episode will also be independently adjudicated by a cardiologist blinded to the study protocol.

A total of 75 patients will be enrolled in the study. After enrollment, patients will have study visits at 1, 6, and 12 months. Six and 12 month follow-up visits will be conducted at these time intervals plus or minus 30 days. If the patient cannot come in for a follow-up visit, then the follow-up may be performed as a telephone interview. During the study visits, patients will be assessed for any interval stroke or TIA-like events, intracerebral hemorrhages, interval medical history, device related complications or other adverse events. At the 1-month visit, a NIH stroke scale score will be obtained. At each study visit, a modified Rankin score will be recorded. There will not be any research labs conducted at these study visits and only blood work associated with routine care may be obtained.

Patients will also have one EP cardiology clinical follow-up visit 10 days (plus or minus 4 days) after device implantation to ensure proper healing of the surgical site and functioning of the device.

At the completion of the study, if there is no clinical reason not to remove the device, then the device will be removed at 1 year from implantation. If there is a clinical indication for longer monitoring, then the device will be kept in longer for a maximum of 3 years. However, if clinical monitoring is required beyond the study period, then monitoring will be performed outside of the

study, and the patient or the patient's insurance will be responsible for any clinical fees associated with this post study monitoring.

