- Movement of the device from its original implant location
- Allergy reactions to the device
- Infection at the site of the implant
- Cosmetic complications at the site of device placement
- Inability of the device to capture some particular arrhythmias
- Risks associated with local anesthesia, including hypersensitivity and allergic reactions to the anesthetic agent, injection site bleeding or infection

POTENTIAL BENEFITS

The presence of paroxysmal AF in non-cryptogenic stroke patients, who have a presumed stroke etiology other than AF, will help in identifying a stroke etiology that carries a high risk for recurrent stroke and will most likely result in a significant management adjustment in terms of long-term anticoagulation for secondary stroke prevention. It is well accepted that long-term anticoagulation of ischemic stroke and TIA patients with paroxysmal AF decreases the incidence of recurrent stroke.

DISCONTINUATION OF STUDY/SUBJECT WITHDRAWAL

Subjects have the right to withdraw from the study at any time without prejudice. The site investigator may withdraw the subject from the study and remove the implantable device in the event of intercurrent illness, adverse events, other reasons concerning the health or well-being of the subject, or in the case of lack of cooperation, non-compliance, protocol violation or other administrative reasons. Participants who regain decisional capacity and do not want the device in their body will also be withdrawn from the study and the implantable device will be removed. This will be discussed in detail during the enrollment and consenting process.

DATA AND SAFETY MONITORING

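### Early device removal is joined to withdrawal from the study, with no provision for continued stroke, hemorrhage, Rankin or safety follow-up of patients who would still accept contact

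*Combined protocol and SAP*

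**What the plan says.** The section Discontinuation of Study/Subject Withdrawal contains two relevant rules.

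- **Discretionary.** The investigator may "withdraw the subject from the study and remove the implantable device in the event of intercurrent illness, adverse events", and also for other health reasons, non-compliance, protocol violation or administrative grounds. Leaving the study and losing the device are described as one step.
- **Mandatory.** The same coupling applies to patients whose capacity returns and who object to the implant. Those who "do not want the device in their body will also be withdrawn from the study and the implantable device will be removed".

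The Follow Up part of the Design section sets the schedule: "After enrollment, patients will have study visits at 1, 6, and 12 months". At these visits "patients will be assessed for any interval stroke or TIA-like events, intracerebral hemorrhages, interval medical history, device related complications or other adverse events", and a modified Rankin score is recorded each time. Attendance in person is not essential: "If the patient cannot come in for a follow-up visit, then the follow-up may be performed as a telephone interview".

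The fourth secondary objective is "Incidence of recurrent ischemic stroke". Under Data and Safety Monitoring, adverse events, which include device complications and new medical conditions, are reviewed every 6 months for relatedness and severity.

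No section describes a patient whose device comes out early but who continues the scheduled visits. No section says whether data are collected after withdrawal, and the Statistical Analysis section has no rule for withdrawn patients.

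**The concern.** The device is needed to detect AF. It is not needed to learn whether a patient has had another stroke or a hemorrhage, to score disability, or to follow a wound infection until it heals. By joining explant to study withdrawal, the plan allows the second kind of information to be lost when only the first kind has become unobtainable.

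Several of the listed triggers are medical events, so patients who leave this way may differ in prognosis from those who stay. Loss of that kind is potentially informative, and the analysis section does nothing to correct it. The outcomes at stake are recurrent ischemic stroke (a secondary objective with few expected events) and the safety record of the implanted device.

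**Working it through.** **1. Is there a figure to reproduce?** No. The 75 patients come without a precision target, power calculation or dropout allowance, and no withdrawal rate is stated. What follows is a sensitivity range, not a check of a planned number.

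**2. Which outcomes could still be collected after explant?**

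| Outcome | Needs the device? | Source under the plan |
|---|---|---|
| AF detection, duration, frequency | Yes | Device transmissions |
| Recurrent stroke or TIA | No | Visit or telephone |
| Intracerebral hemorrhage | No | Visit or telephone |
| Modified Rankin score | No | Visit or telephone |
| Resolution of device complications | No | Visit or telephone |

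**3. Inputs.**
- N = 75 (Follow Up).
- Recurrence risk r = 3.9% or 15.5% (Introduction). The document gives no time frame for these. Reading them as 12-month risks is an assumption.
- Withdrawals w = 4 or 8. This is an assumption: 5% to 10% of 75 is 3.75 to 7.5, rounded up.
- Month of withdrawal t = 6 (half a year lost), with t = 1 as the unfavourable case. This is an assumption.

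**4. Formula.** With a constant hazard over 12 months, the expected number of patients whose first recurrence falls after withdrawal is

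missed = w × [(1 − r)^(t/12) − (1 − r)].

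A patient withdrawn because of a recurrent stroke is already counted and does not enter this number.

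**5. Half a year lost (t = 6).**
- r = 3.9%: √0.961 − 0.961 = 0.9803 − 0.9610 = 0.0193. Times 4 = 0.08; times 8 = 0.15.
- r = 15.5%: √0.845 − 0.845 = 0.9192 − 0.8450 = 0.0742. Times 4 = 0.30; times 8 = 0.59.

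The range is about 0.1 to 0.6 missed strokes. Over 75 patients that is 0.08/75 = 0.1 to 0.59/75 = 0.8 percentage points.

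**6. Unfavourable case (t = 1, w = 8, r = 15.5%).** 0.845^(1/12) − 0.845 = 0.9861 − 0.8450 = 0.1411. Times 8 = 1.13 missed strokes.

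If the other 67 patients have 3.9% risk, the expected total is 67 × 0.039 + 8 × 0.155 = 2.61 + 1.24 = 3.85, or 5.1% of 75. The observed figure would be (3.85 − 1.13)/75 = 3.6%. The undercount is 1.13/3.85 = 29% in relative terms and 1.5 percentage points in absolute terms.

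**7. Scale.** Without any loss, expected recurrences are 75 × 0.039 = 2.9 to 75 × 0.155 = 11.6. The exact 95% interval for 3/75 is 0.8% to 11.2%, so sampling error is far larger than the bias in any of these scenarios.

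**The case against.** The case for leaving the text alone has four parts.

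- **The main clause is a permission.** It says the investigator *may* withdraw the patient. It sets no severity threshold and does not say that every explant ends participation. A reader might infer that patients with the worst events automatically leave on the day of the event. The text does not support that. The only mandatory coupling concerns patients who regain capacity and decline the device, which is a matter of consent and not of safety. This part of the objection stands.
- **The triggering event is not lost.** The investigator who acts on it knows of it, and the safety review covers it. A reader might infer that a stroke or hemorrhage leading to withdrawal goes uncounted, but the document gives no ground for that. Only its outcome, or a later event, is exposed. This also stands.
- **Loss after withdrawal is inferred from silence.** The document does not say that data collection stops, so it is correct to say that data may be lost, not that they will be. Still, withdrawal from a study ordinarily ends its visits and nothing here provides otherwise. Because the outcome is left to individual discretion, a sentence is worth adding.
- **The effect is small and secondary.** This is a single-arm descriptive cohort with no treatment comparison to distort, recurrent stroke is the fourth secondary objective, and the primary endpoint needs the device. A reader might expect one or two missed strokes (1/75 = 1.3 to 2/75 = 2.7 points). With 4 to 8 withdrawals and half a year lost each, the expected number stays below one. This limits the importance of the point but does not remove it.

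**Conclusion.** The point holds as a gap in the design with a small expected effect. The plan permits, and in one situation requires, study withdrawal together with device removal, and it provides no continued follow-up for outcomes that remain obtainable. Later strokes, hemorrhages, Rankin scores and the resolution of device complications may therefore be missed, possibly in a way related to prognosis.

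For recurrent stroke, the range in the working is below one expected event under even loss over time. It passes one only when early loss is concentrated in high-risk patients. These sizes depend entirely on an assumed withdrawal rate, an assumed timing, a constant hazard, and the reading of the cited recurrence figures as 12-month risks. Hemorrhage and Rankin losses cannot be sized from the document.

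A reader might also take this as a threat to the primary AF incidence that the remedy would cure. It would not: visits or calls after explant recover no rhythm data. How patients without full monitoring enter the AF denominator and the Kaplan-Meier analysis is a separate question.

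**What to change.** Separate the end of device monitoring from the end of study follow-up in the withdrawal section, along these lines:

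- If the device is removed or monitoring stops for any reason other than withdrawal of consent to contact, the patient remains in the study for the remaining scheduled visits, by telephone where needed.
- Reporting of device- or procedure-related adverse events continues until resolution or stabilization.
- The date and reason are recorded separately for the end of monitoring and for the end of follow-up.
- Withdrawal from the study is reserved for patients who withdraw consent to contact. A patient who regains capacity and declines the device is asked whether contact may continue.

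Decisions on when a device is removed are unchanged. The cost is an amendment to the protocol and consent wording, plus a few contacts that the schedule already includes.
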